8.3 Stability of LorelcoTM

LorelcoTM capsules (250 mg) are to be stored at room temperature in sealed conditions. Current stability data indicates that the capsules are stable when stored as described for up to 36 months.

8.4 LorelcoTM Study Drug Packaging and Labelling

LorelcoTM 250 mg capsules will be provided to sites in Webster packs from Oxford Compounding.

The label will include the following information. The clinical trial material will be clearly marked according to national requirements regarding use for clinical trial investigation only and will be labelled with the drug name, study reference number, and storage conditions.

It will be the responsibility of the investigator to ensure that accurate accountability records are maintained throughout the study. The pharmacy will prepare and dispense the

Protocol Version 4, 06 OCT 2021

Confidential

Page 32 of 70

investigational product according to the randomization scheme.

Individual dosing containers will be labelled by the investigational site with the following:

- "For Clinical Trials Use Only"
- Protocol Number
- Principal Investigator Name
- Subject name and subject number/ Randomization No.
- Dosing directions
- Name of Sponsor and Contact Details
- Batch Number
- Expiry Date
- Storage Conditions
- Keep in a cool, dark place (avoid light exposure)
- Keep out of reach of children

All investigational products will be packaged and labelled. Labelling of the investigational products will be performed in accordance with Annex 13 of the Good Manufacturing Practices for investigational products labelling requirements.

Detailed instructions for the preparation labelling and supply of LorelcoTM capsules are described in the study Pharmacy Manual.

8.5 Handling and Storage

Study drug supplies will be stored securely at the site and/or designated Pharmacy according to the State and Commonwealth Laws.

The site Pharmacy must ensure that deliveries of study drug are correctly received by a responsible person, that all receipts of drug shipments are recorded on the appropriate Drug Accountability forms prepared by the site Pharmacy and that all study drugs are stored in a secure area under recommended storage conditions, as listed in this protocol (or the CMI/product information sheet. It is also the responsibility of the PI to ensure that the integrity of packaged study drug not be jeopardised prior to dispensing. Only patients enrolled in the study may receive the study drug(s), in accordance with all applicable regulatory requirements. Only authorised and trained site staff may supply or administer the study drug.

At the scheduled study visits where the patient will consume the study drug at the study site, individual doses will be dispensed by the site Pharmacy staff member on the morning of dosing and recorded in the drug accountability records. Patients will also be provided with appropriate quantity of LorelcoTM for at-home dosing (per the Schedule of Assessments) and will be instructed by study staff on the handling and storage of the study drug(s). The study Pharmacy Manual will define the procedures for dispensing.

8.6 Accountability of Study Drug Supplies

All material supplied is for use only in this study and should not be used for any other purpose.

The PI is responsible for study drug accountability, reconciliation and record maintenance at the study site. In accordance with all applicable regulatory requirements, the PI or designated trained site staff must maintain study drug accountability records throughout the course of the

Protocol Version 4, 06 OCT 2021

Confidential

Page 33 of 70

study. This person will document the amount of Investigational Product received by the site Pharmacy and the amount supplied and/or administered to and returned by patients, if applicable. Used containers of study drug will be retained and sequestered per patient and made available to the study monitor during study drug reconciliation.

The date and time of dose preparation and release will be maintained to support administration of the study drug within the predefined use period. The shipment/receipt/supply records as well as records of dispensing and administration will be verified by a second member of staff. The site Pharmacy will dispense the study drugs to the study site and the study site staff will administer the study medication only to patients included in this study following the procedures set out in the study Pharmacy Manual and in this protocol. Dispensing and supply/administration will be verified by a second staff member. Each patient will be given only the study drug preparation carrying his/her study number. Study drug administration will be documented in the eCRF and other study drug record(s). The PI (or designated trained site staff) is responsible for assuring the retrieval of all left-over study supplies following administration to patients.

The inventory must be available for inspection during the study. When requested in writing by the Sponsor and following drug accountability and reconciliation, unused study drug supplies may be returned to the Sponsor or destroyed by the PI (or delegate), provided destruction does not expose humans to risks from the study drugs. Records shall be maintained of the return or destruction of the study drug. These records must show the identification and quantity of each unit returned or disposed of, the method of destruction (taking into account the requirements of local law), and the person who returned or disposed of the study drug materials. Such records must be submitted to the Sponsor.

Protocol Version 4, 06 OCT 2021

Confidential

Page 34 of 70

9 ADMINISTRATION OF INVESTIGATIONAL PRODUCTS

9.1 Administration of Investigational Products

Delegated study site personnel will supervise and instruct patients on the administration of the Investigational Products.

9.1.1 Investigational Product Administration

The dose and number of 250 mg LorelcoTM or placebo capsules will be administered as described in Table 2. Patients will self-administer investigational product (under the supervision of site staff, or at home) orally, with a full cup (approximately 240 mL) of noncarbonated room temperature water.

Dosing instructions will be detailed in the study Pharmacy Manual and will be provided to the patients at each Investigational Product dispensing.

Orally administered Investigational Products must be swallowed whole and not chewed, divided, dissolved or crushed.

For all drug administrations performed during "at home" periods, participants will self-dose at home unsupervised. Patients will be instructed to return all Webster packs to site staff at each clinic visit for accountability checks. Patients will be instructed not to take the LorelcoTM on clinic visit days until the safety blood samples have been taken.

10 CONCOMITANT MEDICATIONS AND OTHER RESTRICTIONS

Compliance to these restrictions will be assessed prior to first dosing and throughout the duration of the study.

10.1 Concomitant Medications

In general, all supportive measures consistent with optimal patient care will be given throughout the trial. However, the following restrictions apply:

- Any prescription or non-prescription medications that are strong QTcF prolongation inducers (APPENDIX 7) are prohibited within 7 days prior to the first dose administration of LorelcoTM and throughout the study;
- Any prescription and non-prescription medications, herbal remedies, vitamins and nutritional supplements taken by patients must be reviewed and approved by the Investigator.

All concomitant therapies should be recorded in the patient's source documents and corresponding eCRF at each scheduled visit. All medication changes since the last visit will be captured, including new medications, changes in dose or schedule for existing medications, and cessation of medications. For new medications, the dose, route of administration, schedule and indication will be recorded. Dates of changes to medications (commencement, cessation and/or alteration in dose or schedule) will also be captured.

Where possible, any concomitant therapy should be withheld until at least 1 hour following study drug administration on each day.

10.2 Fasting Requirements

Protocol Version 4, 06 OCT 2021

Confidential

Page 35 of 70

Patients will be required to fast for a minimum of 8 hours prior to collection of the safety laboratory blood samples at each visit.

10.3 Supportive Care

The use of supportive care including steroids and antibiotics, will be permitted as clinically indicated and according to institutional guidelines.

Surgeries must be discussed with the Sponsor MM and Investigator prior to determining if patients can remain on study.

10.4 Contraception

Female patients of child-bearing potential, with a fertile male sexual partner, should use highly effective methods of birth control (APPENDIX 6) from signing the consent form until at least 3 months following the last dose of study therapy.

Male patients, who are not surgically or biologically sterile, should use a condom in addition to having the female partner a use highly effective methods of birth control (APPENDIX 6) from signing the consent form until 3 months following the last dose of study therapy.

All study patients must be willing to ensure that corresponding sexual partners practice these same methods of highly effective birth control for the same duration.

Protocol Version 4, 06 OCT 2021

Confidential

11 STUDY PROCEDURES

For the exact timing of each procedure, please refer to the Schedule of Assessments (SoA) in APPENDIX 1. Clinical staff are required to perform assessments at the nominated timepoints within the time windows indicated in SoA. Actual times of procedures for each patient may vary depending on scheduling and will be recorded in the eCRF. In the event of multiple procedures scheduled at the same time, the order, where possible, will be (1) vital signs, (2) 12-lead ECG, (3) safety laboratory blood sampling.

11.1 Informed Consent

The Information and Informed Consent Form (ICF) will be provided to patients at Screening and signed prior to any study procedures being performed. Investigators at each site are responsible for maintaining a record of all patients screened, including both those who enter the study and those who do not.

11.2 Medical History

A full medical history will be obtained at Screening, including a detailed neurologic history, other medical and surgical history, medication history and drug allergies. Demographic data including gender, ethnicity, and race will be recorded.

11.3 Height and Weight

Body height (centimetres) and weight (kilograms) will be measured, and body mass index (BMI) will be calculated. Height should be measured on a wall-mounted stadiometer. Weight should be measured in light-weight clothing, without shoes.

11.4 Pregnancy Test

Female patients (women of child-bearing potential (WOCBP) only) will complete a blood chorionic gonadotropin (hCG) pregnancy test at Screening, Baseline, and again at their EoS visit. A hCG pregnancy test will be conducted at other designated time points as per the SoA. If any of the hCG tests are > 5 U/L but < 25 U/L, a second hCG test will be completed in 7 days. In instances of a positive pregnancy result at any time points, the patient will be withdrawn from the study. Patients withdrawn from the study due to pregnancy may be replaced at the discretion of the PI.

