- 16. Other excluded medications will be those that are;
 - Specifically contraindicated with Probucol, based on historic clinical indications for the treatment of cardiovascular disease. Stable use (for at least 3 months) of cholinesterase inhibitors and memantine will be allowed.
 - Patients on high dose loop-diuretics or thiazide diuretic medications, will be excluded if taking maximum dose of furosemide or Bendroflumethiazide
- 17. Self-reported human immunodeficiency virus (HIV-1 or HIV-2), hepatitis B (HBsAg) or hepatitis C virus (HCV).
- 18. Any inflammatory or chronic pain condition that necessitates regular use of opiates/opioids,
- 19. Major surgery within 28 days of Cycle 1, Day 1, or minor surgical procedures within 7 days of Cycle 1, Day 1. *Exception: no waiting period applies following port-a-cath placement for venous access.*
- 20. For women of childbearing potential, a hCG pregnancy test > 5 U/L at screening, or on Day 1, prior to dose administration.
- 21. Pregnant or breast-feeding (or planning to breastfeed) while on study through 15 days after the last dose of study drug.
- 22. Hypersensitivity or other clinically significant reaction to the study drug or its inactive ingredients.

Protocol Version 4, 06 OCT 2021

Confidential

Page 8 of 70

Curtin University	Study Protocol Protocol No.: PIA-2020
	23. Known substance abuse or medical, psychological, or social conditions that, in the opinion of the Investigator, may interfere with the patient's participation in the clinical study or evaluation of the clinical study
	results. 24. Any other condition or prior therapy that in the opinion of the Investigator would make the patient unsuitable for this study, including inability to cooperate fully with the requirements of the study protocol or likelihood of noncompliance with any study requirements
Overall Study Design Description	This is a Phase 2, randomised, double blind, placebo-controlled parallel group study in adults with mild to moderate AD. The study will assess the efficacy, safety and tolerability of the treatment of Alzheimer's disease subjects with Lorelco TM . After consenting to participate in the study, screening procedures will occur between Days -56 and -1. All subjects must have measurable mild or moderate Alzheimer's disease, and accordingly screening procedures will include:

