- 12. Major surgery is planned during the conduct of the trial, or a clinical event has occurred in the six months preceding study inclusion that may compromise ability to participate for the duration of the study,
- 13. Evidence of stroke,

Protocol Version 4, 06 OCT 2021

Confidential

Page 30 of 70

Curtin University Study Protocol
Protocol No.: PIA-2020

- 14. Current diagnosis with a psychiatric disorder, or taking psychotropic medications,
- 15. Willing and able to undergo Magnetic Resonance Imaging (MRI)
- 16. Other excluded medications will be those that are;
 - Specifically contraindicated with Probucol, based on historic clinical indications for the treatment of cardiovascular disease. Stable use (for at least 3 months) of cholinesterase inhibitors and memantine will be allowed.
 - Patients on high dose loop-diuretics or thiazide diuretic medications, will be excluded if taking maximum dose of furosemide or Bendroflumethiazide
- 17. Self-reported active human immunodeficiency virus (HIV-1 or HIV-2), hepatitis B or hepatitis C virus (HCV) at the Screening visit.
- 18. Any inflammatory or chronic pain condition that necessitates regular use of opiates/opioids,.
- 19. Major surgery within 28 days of Day 1 Week 0, or minor surgical procedures within 7 days of Day 1 Week 0.
- 20. For women of childbearing potential, a pregnancy hCG test > 5 U/L at screening, or on Day 1, prior to dose administration.
- 21. Pregnant or breast-feeding (or planning to breastfeed) while on study through 15 days after the last dose of study drug.
- 22. Hypersensitivity or other clinically significant reaction to the study drug or its inactive ingredients.
- 23. Known substance abuse or medical, psychological, or social conditions that, in the opinion of the Investigator, may interfere with the patient's participation in the clinical study or evaluation of the clinical study results.

Any other condition or prior therapy that in the opinion of the Investigator would make the patient unsuitable for this study, including inability to cooperate fully with the requirements of the study protocol or likelihood of noncompliance with any study requirements

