12.7 Exposure In Utero Management and Reporting

In instances of pregnancies or suspected pregnancies (including a hCG pregnancy test > 25 U/L regardless of age) while a patient is on study treatment, dosing of Lorelco TM (and placebo) must be discontinued immediately. Pregnant patients (or pregnant partners of male patients) should be advised to call their healthcare provider.

The Investigator will notify the Sponsor and designated study Safety Officer of any pregnancy and document the pregnancy on the Exposure in Utero Form as described in the study Safety Reporting Plan.

The Investigator shall obtain informed consent from a pregnant patient (or a pregnant female partner of a male patient) to allow the Investigator (or delegate) to conduct follow-up throughout the gestational period and on the infant following delivery. The Investigator shall follow-up newborn infants that have been exposed to study drug *in utero* for a minimum of 12 months. Upon discovery of any congenital anomalies (or neonatal deaths) the Investigator

Protocol Version 4, 06 OCT 2021

Confidential

Page 47 of 70

shall submit a follow-up report to the Sponsor (or designated study Safety Officer) using an SAE Form (as per the study Safety Reporting Plan) including information regarding the status of the newborn. A miscarriage or abortion shall also be reported by the Investigator to the Sponsor (or the designated study Safety Officer) using an SAE Form.

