13.6 Efficacy Analyses

The primary analysis was an intention-to-treat analysis of all randomized participants. Data will be analysed using both Generalised Estimating Equations (GEE) and Bayesian Analysis. The analysis of primary endpoints will use linear mixed-effects models, with random slopes and intercepts.

The Alzheimer's Disease Assessment Scale's cognitive subscale (ADAS-Cog) is the standard primary cognitive outcome measure for evaluating treatments in clinical trials of mild-to-moderate AD. But the utility of ADAS-Cog is compromised primarily due to some of its items suffering from either floor or ceiling effects in different stages of AD. The current scoring methodology is also sensitive to missing item responses, scoring errors and variability in the administration of the ADAS-Cog, which are common in clinical trials.

The scoring methodology ADAS-Cog as proposed by Verma et al. will be utilised as it significantly improves the sensitivity of the ADAS-Cog in measuring progression of cognitive impairment in clinical trials focused in the mild-to-moderate AD stage²¹. This scoring methodology also provides a boost to the efficiency of clinical trials requiring fewer patients and shorter durations for investigating disease-modifying treatments. For patients with missing responses to certain items, this new scoring methodology does not require data imputation and estimates cognitive impairment using the set of items answered by the patients.

Analysis of all primary and secondary endpoints contrasting Probucol and placebo, after adjusting for covariates, will use mixed effects-regression with 'random' intercepts and slopes (as has been used for power calculations). Mean differences and associated 95% confidence intervals will be presented for the 'fixed' effect of Probucol treatment.

Further analysis investigating the relationship between change scores (post-minus pre-intervention scores) for the primary ADAS-Cog with MRI volumes (total GM, hippocampus, and medial temporal lobe volumes) and specific blood biomarkers (eg: plasma lipoprotein-Aβ) will be considered using Pearson (or Spearman where appropriate) correlation analysis. For all other correlations between recorded variables that lack an a priori hypothesis, control of statistical errors will be carried out using Holm-Sidak corrections for multiple comparisons.

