	Eligibility (including medical history, staging, and concomitant medication usage) to be reviewed, and eligibility confirmed prior to dose administration on Day 1.
--	---

- ² Concomitant medication usage to be reviewed by study staff at each scheduled visit and telephone call
- Full physical examination at Screening and End of Study visit to include, at a minimum, assessment of the following systems: skin, head, ears, eyes, nose and throat, lymph nodes, heart, chest, abdomen and extremities, and a neurological examination (assessment of speech, cranial nerves, motor power, deep tendon reflexes, sensation, coordination and gait), and any other focused assessments suggested by the presence of specific symptoms. All abnormal findings noted at the screening visit should be recorded as medical history.

All other physical examinations will be abbreviated on symptom directed at the discretion of the investigator

- Participants should be resting in a supine position for at least 5 minutes prior to and during vital signs measurements. Vital sign assessments may be repeated once, if abnormal values were recorded in the first instance, at the discretion of the PI.
- ECGs will be taken after at least 5 minutes in a supine quiet rest position. Screening and prior to first dose, triplicate 12-lead ECGs (within 5 minutes, with each reading separated by at least 1 minute) will be taken to establish baseline. The average value for the triplicate will be utilized for assessing QTcF inclusion criteria. Triplicate 12-lead ECGs will also be recorded at the EoS visit. All other post-first dose ECGs will be single readings. In case of evident bad quality (e.g. muscle tremor) of the tracing, the ECG will be repeated.
- For women of childbearing potential only. Testing must be performed, and confirmed negative (hCG \leq 5 U/L), prior to dose administration.
- For women of childbearing potential only. If the hCG blood test is > 5 U/L but < 25 U/L, repeat hCG test will be completed after 7 days.
- Patients are required to fast for a minimum of 8 hours prior to blood sample collection. Water is permitted. Fasting blood tests include serum thyroid, CRP, iron studies, B12, folate, blood sugar, HbA1c and lipids (refer to APPENDIX 5).

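### The hCG rules disagree for results above 5 and below 25 U/L, and on treatment a result of exactly 25 U/L meets neither the repeat rule nor the numeric stop

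*Protocol*

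**What the plan says.** Four parts of the Protocol set hCG thresholds.

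- **Criterion 20** (section 7.3, and in near-identical words in the synopsis) excludes: "For women of childbearing potential, a pregnancy hCG test > 5 U/L at screening, or on Day 1, prior to dose administration". It mentions no repeat.
- **Section 11.4** covers screening, baseline, end of study and the other scheduled tests: "If any of the hCG tests are > 5 U/L but < 25 U/L, a second hCG test will be completed in 7 days". It then takes a patient with a positive result out of the study, without giving a number for *positive*.
- **Appendix 1** attaches two notes to the whole hCG row, which marks screening and Weeks 3, 15, 26, 52, 78 and 91. The first reads "Testing must be performed, and confirmed negative", defines negative as 5 U/L or less, and sets this as a condition of dosing. The second repeats the 7-day retest with the same limits as section 11.4.
- **Section 12.7** stops dosing at once for pregnancies or "suspected pregnancies (including a hCG pregnancy test > 25 U/L regardless of age) while a patient is on study treatment".

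Three other sections bear on the point. Section 11.5.2 lets an out-of-range screening laboratory result be repeated once, up to and including Day -1. Section 6.2 lists pregnancy among the reasons for stopping study therapy. Section 6.7 lets dosing be stopped for laboratory changes that pose a significant health risk, or on the Investigator's judgement.

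**The concern.** These rules exist to limit fetal exposure to the study drug, so staff should be able to read off one action for any hCG value. For a result between the two cut-offs of 5 and 25 U/L they cannot. Before the first dose, one passage excludes the woman and another sends her for a retest. On treatment, one passage appears to withhold the dose, one orders a retest without mentioning dosing, and the numeric stop is not reached. Up to two sites are planned, and they could act differently on the same result while each following the text.

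The disposition after a positive test is also unclear. Section 11.4 ends participation in the study, section 6.2 ends study therapy, and section 12.7 discontinues dosing and provides for pregnancy follow-up.

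**Working it through.** No sample size, power or error rate is involved, and the plan gives no figure to reproduce. The check applies each written inequality to each band.

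| hCG (U/L) | Criterion 20 (screening, Day 1) | 11.4 and second Appendix 1 note | First Appendix 1 note | 12.7 numeric stop (on treatment) |
|---|---|---|---|---|
| 5 or less | not excluded | no repeat | negative | not met |
| above 5, below 25 | excluded | repeat in 7 days | not negative, no dose | not met |
| exactly 25 | excluded | not met (25 < 25 is false) | not negative, no dose | not met (25 > 25 is false) |
| above 25 | excluded | no repeat | not negative, no dose | met |

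**Before the first dose.** Take 12 U/L. Criterion 20 excludes (12 > 5), and section 11.4 retests (5 < 12 < 25). At screening, section 11.5.2 offers a partial way through: repeat once by Day -1, then judge eligibility. For a Day 1 result that allowance has expired, and no passage says whether a repeat of 5 U/L or less restores eligibility.

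**On treatment.** Take 12 U/L at Week 15. The outcome depends on the scope of the first Appendix 1 note.

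- If it applies at every test in its row, as its placement on the row label suggests, the dose is withheld. Section 11.4 does not say so, and the 12.7 number is not met (12 > 25 is false).
- If it applies only before the first dose, no passage gives a dosing instruction for the 7-day wait.

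**Length of the unresolved period.** Table 2 gives two capsules a day from Week 4, so 7 × 2 = 14 capsules. In Week 3 it gives one a day, so 7 × 1 = 7 capsules.

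**Exactly 25 U/L.** Before the first dose, criterion 20 covers it (25 > 5). On treatment, both limits are strict, so neither a repeat nor the numeric stop is triggered. If the first Appendix 1 note applies at every test, it would still withhold the dose, but with no retest specified.

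**The meaning of *positive* in section 11.4.** The document writes down two candidate cut-offs.

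- If positive means not negative under the Appendix 1 note, it is above 5 U/L. Section 11.4 then both retests and withdraws a woman with 12 U/L.
- If it follows section 12.7, it is above 25 U/L, and exactly 25 U/L triggers nothing in section 11.4.

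**The case against.** The best defence is that most of these passages fit one sequence: withhold the dose, retest in 7 days, then decide. Criterion 20 and the first Appendix 1 note share the 5 U/L cut-off. Section 11.4 and the second note state the same repeat rule. In section 12.7 the figure of 25 U/L is introduced as an example of suspected pregnancy, so an Investigator could stop dosing at a lower value or at exactly 25, and section 6.7 also leaves room for judgement. Section 11.5.2 eases the conflict at screening.

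Much of this stands, and it limits the point. It does not remove it. The sequence is not written anywhere, section 11.5.2 cannot reach a Day 1 result, and discretion does not secure the same action at both sites. A reader may also take 25 U/L or more as positive by elimination, but no passage says so.

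Three stronger readings are tempting, and the Protocol does not support them.

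- *Four mutually incompatible consequences.* There are two cut-offs and one exclude-or-retest conflict, spread over four places. A result of 5 U/L itself is negative under every rule.
- *Dosing is permitted above 5 U/L.* No passage permits it. That reading rests only on the silence of sections 11.4 and 12.7.
- *A randomised woman is removed from the intention-to-treat comparison.* Section 11.4 does say "Patients withdrawn from the study due to pregnancy may be replaced at the discretion of the PI", but recruiting a replacement does not delete the first participant. Section 13.6 states "The primary analysis was an intention-to-treat analysis of all randomized participants", and section 6.8 keeps data collected up to withdrawal.

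**Conclusion.** The point holds as a wording conflict in a safety rule. Three defects can be shown from the text:

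1. Precedence between exclusion and retest is not stated for a Day 1 result above 5 and below 25 U/L.
2. There is no single dosing instruction for that band on treatment while a repeat is awaited. The wait spans up to 14 capsules, or 7 in Week 3.
3. *Positive* has no stated cut-off, and on treatment exactly 25 U/L lies outside both the repeat band and the numeric stop.

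The Protocol does not say how many women of childbearing potential it expects. That they will be few is an assumption, although the criteria admit them from age 18. No efficacy estimate, sample size or error rate changes. The capsule counts assume that dosing follows Table 2 and that the repeat is done on day 7.

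**What to change.** Reconcile criterion 20 (synopsis and section 7.3), section 11.4, both Appendix 1 hCG notes and section 12.7 into one rule, stated once and cross-referenced. For each band, with 5 and 25 U/L explicitly assigned, it should state:

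- whether the woman is eligible, and whether a repeat can restore eligibility on Day 1;
- whether dosing continues or is held while a repeat is awaited;
- what value counts as positive.

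State whether the first Appendix 1 note applies at every scheduled test or only before the first dose. Also reconcile the three descriptions of what follows a positive test: leaving the study (11.4), ending study therapy (6.2) and discontinued dosing (12.7). Which cut-offs and which management apply is for the sponsor's clinicians, and this review does not prefer one passage over another.

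The cost is a wording amendment, with no added tests, visits or patients. Because it touches a safety rule, it may count as substantial under section 18.3 and need ethics approval, so it could be bundled with the next amendment.
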